This investigation does not involve a novel CI or a modification of an existing implantable device. The CIs to be used in this study are physically and technologically unchanged and have current FDA approval (Ultra MS: Model# CI-1600-04, FDA PMA Approval Number P960058/S117; Ultra Slim J: Model# CI-1600-05, FDA PMA Approval Number P960058/S121). Utilization of the device in the diagnosis and treatment of disease (i.e., hearing loss) is also unchanged and consistent with existing FDA-approved indications.

ECochG systems themselves are not novel and have been in clinical use for many years. ECochG devices are FDA-cleared Class II devices. An FDA 510(k) clearance letter is provided (See Appendix). Use of ECochG for the purposes described here is consistent with indications covered under this FDA 510(k) clearance.

The objective of this study is to learn about how ECochG-based observations during conventional CI surgery can improve outcomes compared to the standard-of-care technique of blind electrode insertion. Two clinically relevant outcomes will be considered: post-operative electrode location (i.e., correct electrode placement within the scala tympani) and hearing performance (i.e., postoperative audiometric thresholds in clinic).

Significance

Compared with previous relevant work, whereby ECochG was recorded **near** the cochlea **before** and **after** CI electrode insertion, recording ECochG from the vantage point of the CI's apical electrode **within** the cochlea **during** CI electrode insertion has the advantage of closer proximity to the ECochG signal generators (i.e., cochlear hair cells and the acoustic nerve). This approach has been shown to result in larger amplitude recording, and, thereby, more immediate feedback to the surgeon should these potentials change. An added advantage of this method is that it does not involve any change to the CI device itself, to the way the device is used, or to the surgical technique to place the device.

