This condition is identical to the current standard-of-care for conventional CI surgery used worldwide. The surgeon will perform his or her electrode insertion without ECochG monitoring. Minute manipulations of the electrode are a normal part of conventional electrode insertion; manipulations such as redirecting the insertion vector or slowing down insertion speed will be made, as deemed necessary by the surgeon. A full electrode insertion will be performed, as appropriate. The ECochG responses will be recorded, but the surgeon will be blinded to this information during surgery.

Arm 2: Audible ECochG Response On

This condition will have the audible ECochG response on and available to the surgeon. In this condition, the surgeon perform a conventional electrode insertion while listening to the running ECochG signal for drop in amplitude (suggesting impending trauma). If no drop is detected, insertion will proceed to the full electrode length according to the standard-of-care. If an ECochG amplitude drop is observed, the surgeon will place this observation in its clinical context and evaluate insertion parameters, (i.e., insertion vector, insertion speed, etc.), customary practice with conventional CI surgery, but here

supplemented by the ECochG response. In the case of an ECochG amplitude drop that does not recover, the standard-of-care practice of achieving a full electrode insertion will be followed.

Protocol timeline

1) Pre-Operative (typically 1-30 days before surgery)

- a) Standard counselling regarding CI study; collect consent form for adults or assent form for pediatric participants; collect data release forms.
- b) The surgeon makes his or her CI electrode selection between two options: (1) the HiFocus SlimJ (lateral wall array) or (2) the HiFocus MidScala. Electrode selection is a normal component of conventional CI surgery. All CIs models to be utilized in this study are FDA-approved and will be used within their approved indications (Ultra MS: Model# CI-1600-04, FDA PMA Approval Number P960058/S117; Ultra Slim J: Model# CI-1600-05, FDA PMA Approval Number P960058/S121).
- c) Pure tone audiometry (standard-of-care pre-operative CI candidacy evaluation). In pediatric patients, for whom completion of pure tone audiometry may be difficult or unreliable, auditory brainstem response (ABR) testing can be used to supplement or estimate behavioural thresholds.
- d) Pre-operative CT scan (standard-of-care) for surgical planning.

2) Day of surgery

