- a) Ensure that no cerumen or surgical preparation fluid is in the external ear canal. Place the ear piece in the external ear canal and fold the pinna forward, as in the conventional procedure.
- b) Enter the pre-op audiogram into the software.
- c) Normal CI surgical approach. A conventional round window or extended round window entry into the cochlea is prepared.
- d) Measure ECochG in response to a 500 Hz tone burst stimulus, at 110 dB SPL, during insertion of the CI electrode and after insertion of the CI electrode. Figure 2 schematically depicts the intraoperative set-up. Figure 3 shows the non-invasive surface electrode and earphone array used in ECochG. Figure 4 shows the enclosure box and monitoring screen.
 - i) For participants randomized to Arm 1 of the study, the surgeon will perform CI electrode insertion without ECochG feedback.
 - ii) For participants randomized to Arm 2 of the study, the surgeon will make insertion modifications as appropriate in response to ECochG feedback.

3) Initial CI Activation Visit (3-5 weeks after surgery)

- a) Audio Assessment
 - i) Unaided pure tone audiometry in the implanted and the unimplanted ear
 - ii) Bone-conduction thresholds when possible, depending on the patient's residual hearing status

- iii) For pediatric patients, unaided audiometric data may be collected as tolerated, across different visits, to accommodate the unique challenges of hearing assessment of young children.
- b) **Measure ECochG responses in clinic** (to coincide with audiology, +/- 1 week)
 - i) 125-2000 Hz (frequency scan)
 - ii) At an acoustic intensity level at or below their comfortable level through an insert earphone
 - iii) Directly through the CI
- c) Post-Op CT scan to identify CI electrode scalar location
 - i) Obtain scan within one month following surgery
 - ii) Patient identifiers removed from CT scan data and sent to collaborators in DICOM format for analysis (See Appendix 1).

4) Approximately 3 Month Visit

- a) Audio Assessment
 - i) Pure tone unaided audiology in the implanted and the unimplanted ear
 - ii) Bone-conduction thresholds when possible, depending on the patient's residual hearing status
- b) Measure ECochG responses in clinic (to coincide with audiology, +/- 1 week)
 - i) 125-2000 Hz (frequency scan)
 - ii) At an acoustic intensity level at or below their comfortable level through an insert earphone
 - iii) Directly through the CI

5) Approximately 12 Month Visit

- a) Audio Assessment

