 - i) Pure tone unaided audiology in the implanted and the unimplanted ear
 - ii) Bone-conduction thresholds as appropriate
- b) Measure ECochG responses in clinic (to coincide with audiology, +/- 1 week)
 - i) 125-2000 Hz frequency scan
 - ii) At an acoustic intensity level at or below their comfortable level through an insert earphone
 - iii) Directly through the CI

Detailed description of measurements and procedure

Pure tone and bone-conduction audiology

Pure tone audiology will be performed following the conventional, routine protocol currently in place for determining CI candidacy. Where possible, pure tone thresholds will be established in the implanted ear for 125, 250, 500, 750, 1000, 1500, 2000, 3000, 4000, 6000, and 8000 Hz. Testing will be conducted using insert earphones, and where indicated, the contralateral ear will be masked. Both the implanted and the non-implanted ear will be measured. If clinically appropriate, bone-conduction testing will be performed as well following conventional practices. For young children in our cohort, for whom

hearing testing can be uniquely challenging, thresholds obtained across more than one visit will be permitted and thresholds may be estimated base on auditory brainstem response (ABR) testing.

In line with the Minimum Reporting Standards for Adult Cochlear Implantation recommendations [11], in patients with functionally relevant pre-operative low frequency pure tone averages (125, 250, 500 Hz) < 80 dB HL, post-operative residual hearing will be reported. Each frequency will be reported individually (125, 250, 500, 1000, 1500, 2000, 4000, and 8000 Hz) rather than as a pure tone average.

Electrocotileography

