The implant, sound processor, and the clinical programming interface (CPI) hardware are all FDA-approved, and their use in the study is not associated with any additional risk to the patient. ECochG devices are FDA-cleared Class II devices. For an example of an FDA 510(k) clearance letter for the Otometrics device (k143670), please see Appendix. The ECochG recording software is not FDA/*Conformité Européenne* (CE) certified, but it has been thoroughly tested per AB's internal quality system. The recording software is not part of the CI operation and does not introduce any new or changed risk to the patient. It has been verified that the experimental software does not affect the performance of the FDA-approved software or hardware. Further, the entire protocol detailed above has been utilized and reported upon across several institutions validating the feasibility, ease, and safety of this modification to the convention "no feedback" approach to CI electrode insertion. This study's principal investigator (PI) also has experience using the current system.

Data Acquisition and Storage

Post-operative audiometric measurements and post-operative CT scan results will be recorded in the participant's study binder. Results of intra-operative and post-operative ECochG will be saved by the ECochG software program but will also be printed and kept in the participant's binder. All files will be archived. The main study results will be transferred to Excel-files for analysis. Further analyses will be done with Excel, Matlab or statistical software packages. A member of the Biostatistics Department will assist in statistical analysis. All results will be made anonymous prior to being shown to any third party. It will not be possible for any individual study participant to be recognized from his or her study data.

In addition, we will compare ECochG-based predictions associated with CI electrode scalar position and hearing outcomes to predictions made based on conventional demographic and audiometric data. To facilitate multivariate analysis, we will extract biographical (e.g., age, etiology of hearing loss, duration of deafness) and surgical (e.g., device and electrode type) factors from the electronic medical record.

Statistical Analysis

Randomization

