Block randomization is statistical strategy to prevent unequal numbers of participants from being randomized to one arm vs the other (here, audible signal "on" versus audible signal "off"). For example, using a random number generator set to individually assign 100 participants to one of two groups, there is no assurance that an equal numbers of study participants would end up in the "audible signal on" group, resulting in an unbalanced overall sample, despite randomization of each participant.

Using a block approach, the total sample is divided into smaller blocks and randomization is performed within each block with the rule that the number of allocations is balanced within that block. In our study, although each institution will likely only contribute about 40 participants, we have designed a randomization schedule to allow for 100 participants to be run for each program. This sample of 100 was divided into 50 blocks of two participants; the two participants are randomized ensuring that one goes into the "signal off" group and one goes to the "signal on" group.

Power Analysis

To ensure that our study is appropriately powered to detect a significant difference in the primary outcomes measures, we performed a power analysis with the assistance of a biostatistician. Post-operative CT-based indication of scalar position is treated as a dichotomous variable (i.e., either in the scala tympani or in the scala vestibuli); post-operative hearing outcomes are treated as a continuous variable.

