Scalar Dislocation: Preliminary data indicates that the current state of CI electrode dislocation from the scala tympani to the scala vestibuli is approximately 35% (or, a “successful” scala tympani position is achieved at a rate of 65%). For participants randomized to “ECochG audible signal on,” our expectation, driven by preliminary data, is to decrease the rate of scalar dislocation to approximately 15% (or, a “successful” scala tympani position rate of 85%). Setting the alpha error rate at 2.5%, a total sample size of 192 participants, or 96 participants in each of the two randomization groups, was determined using a Fischer exact test. If we permit a 5% error rate, the total sample size drops to 162 patients (81 randomized to audible signal “on”; 81 randomized to signal “off”). While these numbers of participants are higher than would be possible to achieve at our site alone in an average two-year period, through a coordinated effort to pool multi-center data, it will be easily achievable.

Secondary Planned Analysis

Electrode Type: As detailed above, once a participant is enrolled in the study, the surgeon will select which of two CI electrodes are most appropriate. A secondary analysis comparing scalar position and hearing preservation outcomes will be performed (i.e., four total between-group analyses) between the two electrode groups.

Pediatric Participants: This study will include both adult and pediatric participants. A secondary analysis comparing scalar position and hearing outcomes between adult and pediatric participants will be performed (again, four total between-group analyses).

Regression Analysis: To model the influence of “ECochG on” on the primary outcome measures in the context of participant age group and electrode choice, two regression analyses will be performed – one for the outcome measure of scalar position and one for hearing outcomes.

Hospital Effect Analysis: To determine if there is a meaningful difference in outcome measures across the different participating hospital settings, a secondary analysis will be performed as well.

Safeguarding of Protected Health Information (PHI)

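### The hearing regression by arm names age group and electrode choice but not the pre-operative threshold already collected, so it gives up some precision

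*Protocol*

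**What the plan says.** The Regression Analysis paragraph under Secondary Planned Analysis plans two models, one for scalar position and one for hearing. Each is to estimate the influence of the audible-on arm "on the primary outcome measures in the context of participant age group and electrode choice". No other covariate is named.

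The Objectives section gives the second outcome as "hearing performance (i.e., postoperative audiometric thresholds in clinic", and the Power Analysis section adds that "post-operative hearing outcomes are treated as a continuous variable".

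The baseline is available. The pre-operative step of the Protocol timeline lists "Pure tone audiometry (standard-of-care pre-operative CI candidacy evaluation", and for children it allows that "auditory brainstem response (ABR) testing can be used to supplement or estimate behavioural thresholds". The day-of-surgery step says "Enter the pre-op audiogram into the software". A 500 Hz threshold is also an inclusion criterion.

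Pre-operative hearing or audiometric data have two further uses. The section on pure tone and bone-conduction audiology uses the low-frequency average to decide whose residual hearing is reported, and there "Each frequency will be reported individually". Data Acquisition and Storage sets ECochG-based predictions against "predictions made based on conventional demographic and audiometric data"; the factors it then extracts for multivariate work are biographical and surgical. Neither use adjusts the comparison of arms.

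**The concern.** A pre-operative threshold in the same ear at the same frequency is the measured variable most directly tied to the post-operative threshold. A model that adjusts for age group and electrode but not for this value leaves between-patient differences in starting hearing in the residual, which widens the confidence interval for the arm effect.

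This matters more for hearing than for scalar position. None of the four numbered hypotheses is an arm difference in hearing, so this regression is where the protocol states a model for that comparison. The sample size was set on scalar position and no figure is given for hearing, so precision for hearing is not secured by design.

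The point concerns only the randomised arm comparison, not the contrasts between electrodes or between adults and children.

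**Working it through.** **The plan's own figure.** The protocol gives dislocation rates of 35% and 15%, Fisher's exact test, and 96 per arm at alpha 2.5% or 81 per arm at 5%. Power and sidedness are not stated. By full enumeration, two-sided Fisher power is 80.7% at 96 per arm (alpha 0.025) and 80.2% at 81 per arm (alpha 0.05). The totals of 192 and 162 therefore reproduce as two-sided designs with 80% power. They concern scalar position only.

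**Inputs for hearing.** The outcome is continuous, allocation is 1:1, and the named covariates are age group and electrode. Let r be the correlation of pre- and post-operative thresholds given arm, age group and electrode. The protocol states neither r nor an SD, so a range of r is assumed.

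**Formulas.** With N participants and residual SD σ, the variance of the arm effect is approximately:

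- raw post-operative threshold: 4σ²/N
- change score, equal pre and post SDs: 4·2σ²(1 − r)/N
- baseline as covariate: 4σ²(1 − r²)/N

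The covariate model has variance 1 − r² relative to raw thresholds. Relative to a change score it is (1 − r²)/[2(1 − r)] = (1 + r)/2.

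| Assumed r | Variance vs raw, 1 − r² | CI width vs raw, √(1 − r²) | Raw-analysis N matched by 192 adjusted, 192/(1 − r²) | Variance vs change score, (1 + r)/2 |
|---|---|---|---|---|
| 0.2 | 0.96 | 0.980 | 200 | 0.60 |
| 0.3 | 0.91 | 0.954 | 211 | 0.65 |
| 0.5 | 0.75 | 0.866 | 256 | 0.75 |
| 0.7 | 0.51 | 0.714 | 376 | 0.85 |

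The variance ratios hardly depend on how many thresholds prove analysable.

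**Noisy baselines in children.** Assume a quarter of participants have ABR-estimated baselines with reliability 0.6 (neither figure is in the protocol). The attenuation factor is 1/[1 + 0.25 × (1/0.6 − 1)] = 1/1.167 = 0.857. The ratio against raw thresholds becomes 1 − 0.857r² = 0.966, 0.923, 0.786 and 0.580, so the cuts are 3%, 8%, 21% and 42%.

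**Cost of the covariate.** With four coefficients already in the model (intercept, arm, age group, electrode), one more covariate inflates the variance by about 1/(n − 6). This is 1/186 = 0.54% at n = 192, and 1/114 = 0.88% at an assumed n of 120. Break-even is r = √[1 − 1/(1 + cost)] = 0.073 and 0.093.

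**Simulation check.** In 4,000 runs with age group and electrode in every model and r = 0.3, 0.5, 0.7, the ratios against raw thresholds were 0.90, 0.74, 0.51 at n = 192 and 0.91, 0.76, 0.50 at n = 120. Against change scores at n = 192 they were 0.67, 0.75, 0.85. With the ABR noise, the ratios against raw thresholds at n = 192 were 0.94, 0.80, 0.58. These agree closely with the formulas.

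**The case against.** The strongest objection is that covariate lists for secondary regressions usually belong in the statistical analysis plan, which was not available. The paragraph does not close its list, and the section on data acquisition shows that the investigators intend to use audiometric data in modelling. This limits the force of the point but does not remove it. The protocol is not silent on covariates: it names two and omits the most obvious one, and the audiometric data it mentions serve a comparison of predictions rather than of arms.

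Second, the outcome may be change from baseline, since the Electrode Type paragraph speaks of preserved hearing. Baseline would then already be used. No change score is defined, however, and under equal SDs the covariate model still gains, because (1 + r)/2 is below 1 whenever r is below 1.

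Third, the size rests entirely on assumed values. The entry limit of 80 dB HL at 500 Hz restricts the spread of baselines and could push r down; at r = 0.2 the interval against raw thresholds narrows by only 2%. This stands, and no particular gain should be promised.

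Fourth, the visit and frequency for this regression are not set, so a same-frequency covariate presumes a choice not yet made. That is fair, but the wording fits whichever frequency is modelled.

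**Conclusion.** The point holds as a modest improvement. The stated hearing model omits a baseline that is already measured, and any appreciable correlation between pre- and post-operative thresholds makes that a loss of precision. Against raw thresholds the avoidable variance is 4% to 49% for r between 0.2 and 0.7, or 3% to 42% under the assumed ABR noise. Against a change score with equal SDs it is 40% down to 15% over the same range. The true figure cannot be found from the protocol. The covariate pays for itself once r exceeds about 0.07 (192 analysable thresholds) or 0.09 (120).

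There is no bias in the randomised comparison and no consequence for the 192. Confidence is medium, because an analysis plan not seen here may already include the covariate.

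**What to change.** Add one sentence to the Regression Analysis paragraph: the hearing model for arm will include, besides age group and electrode choice, the implanted ear's pre-operative threshold at the same frequency as the outcome. State also that a participant with no baseline at that frequency stays in the model, with the value filled in by a rule that takes no account of arm. Limit the change to the arm comparison, and settle it before outcome data are seen so that the covariate is not chosen after the fact.

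The cost is one degree of freedom (about 0.5% in variance at 192), some noise where children's baselines are ABR-estimated, and the need to write the missing-baseline rule. No new measurement, extra participant or change in conduct is required.
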